9.2 Response Criteria

Г

Evaluation of Tar	get Lesions
Complete Response (CR)	Disappearance of the target lesion; ideally, this determination will be made based on CT image evaluation.
Partial Response (PR)	At least a 30% decrease in the LD of the target lesion, taking as reference the baseline LD; ideally, this determination will be made based on CT image evaluation.
Stable Disease (SD)	Neither sufficient shrinkage to qualify for CR/PR above nor sufficient increase to qualify for LE below, taking as reference the smallest LD since the treatment started
Local Enlargement (LE)	At least a 20% increase in the LD of target lesion, taking as reference the smallest LD recorded since the treatment started; Ideally, this determination will be made based on CT image evaluation.
Local Failure (LF)	Refers to the primary treated tumor after protocol therapy and corresponds to meeting both of the following two criteria: 1) Increase in tumor dimension of 20% as defined above for local enlargement (LE); 2) The measurable tumor with criteria meeting LE should be avid on Positron Emission Tomography (PET) imaging with uptake of a similar intensity as the pretreatment staging PET, OR the measurable tumor should be biopsied confirming viable carcinoma. For outcome analysis, Marginal Failures (MF; see below) will also be counted as LF; however, they should be distinguished specifically as MF, not LF, on all report forms. The EORTC criteria for post-treatment PET evaluation will be used as a basis for evaluation in cases more difficult to assign as to whether the uptake is pathological for cancer recurrence vs. inflammation. ⁴⁶
Local Control (LC)	The absence of Local Failure.
Progressive Disease (PD)	Progression will be defined by any

imaging and clinical findings which
support development of disease outside
the chest, in the mediastinum or first
echelon lymph nodes, and by PET +/-
biopsy consistent with progression at the
target lesion.

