7.0 STUDY CALENDAR

	Pre- Treatment ¹¹	Rx #1 ¹⁰	Rx #2	Rx #3 ⁹	6 wks post- rx	12 wks post- rx	f/u ^{1,11}
H&P ⁸	X	Х	Х	Х	Х	Х	Х
Performance Status	X	X	X	X	X	Х	Х
Evaluation by Thoracic Oncologist	X						
Evaluation by Radiation Oncologist	X						
Pregnancy test	X						
CT C/A/P ⁷	X						
PET-CT scan ⁷	Х						X ²
PFT's ⁶	X						X ³
Tumor Biopsy	X						X4
Blood and urine, collection for DBBR, future analyses ⁵	X						
Toxicity Eval	X	Х	Х	Х	Х	Х	Х
QOL questionnaire	X	X	X	X	X	X	X

¹ At week 6 and 12 post SBRT as noted above, then every 3 months for 1 year, and every 6 months for the next 4 years. Patients will be followed for a total of 5 years.

² PET-CT will be done at 6 months and then as clinically indicated

³ PFTs will be done at 6 months, and annually in follow-up

⁴ Biopsies will be done only if clinically indicated.

⁵Blood and urine will be collected through the DBBR at pre-treatment. Patients may refuse this and still participate in the study. This will not be offered at network sites.

⁶ Full Spirometry and DLCO

⁷ Any one of these pre-treatment imaging studies should be done within 6 weeks of registration: CT Chest, PET or CT Simulation

⁸ H&P within 2 weeks of treatment start

⁹Overall treatment time for one fraction is one day, for three fractions is 8-24 days.

¹⁰Treatment may start within 4 weeks after registration.

¹¹Pre-treament and follow up assessments may be waived at the discretion of the Principal Investigator.

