9.1 Baseline documentation of "Target" and "Non-Target" Lesions

Patients enrolled to this protocol should have clinical stage I (T1 or T2, N0, M0) or clinical stage II (non-small cell lung cancer. At time of treatment, they should only have one site of gross disease in the lung with no metastases. The primary lung tumor should be identified as the *target lesion* and recorded and measured at baseline and with each follow-up imaging evaluation.

The longest diameter (LD) for *the target lesion* will be calculated **from the treatment planning CT scan** using pulmonary windowing and reported as the baseline LD. The baseline LD will be used as reference by which to characterize the objective tumor. For follow-up assessment, diagnostic CT scans performed using a 5 mm contiguous reconstruction algorithm using pulmonary windowing taken as part of scheduled protocol follow-up are preferred as the method of evaluation for response. When CT scans are not available, chest x-ray determination will be allowed as long as the target lesion is clearly visible. Changes in serum tumor markers will not be allowed for assessment of either local tumor progression or metastatic progression.

Local treatment effects in the vicinity of the tumor target may make determination of tumor dimensions difficult. For example, bronchial or bronchiolar damage may cause patchy consolidation around the tumor that over time may coalesce with the residual tumor. In cases where it is indeterminate whether consolidation represents residual tumor or treatment effect, it should be assumed that abnormalities are residual tumor. A treating radiation oncologist will review films as well as a radiologist at each site.

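### Section 9.2 scores an enlarged target that is never tested by PET or biopsy as locally controlled, and only one follow-up PET-CT is scheduled

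*Combined protocol and SAP*

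**What the plan says.** The table in Section 9.2 builds the local outcome in three steps.

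- **Local Enlargement (LE):** "At least a 20% increase in the LD of target lesion, taking as reference the smallest LD recorded since the treatment started".
- **Local Failure:** it "corresponds to meeting both of the following two criteria". The first is growth as for LE. The second is that the target "should be avid on Positron Emission Tomography (PET) imaging with uptake of a similar intensity as the pretreatment staging PET", or, as the alternative, that "the measurable tumor should be biopsied confirming viable carcinoma".
- **Local Control:** "The absence of Local Failure".

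The tests that can satisfy the second criterion are set out in the Study Calendar (Section 7.0). Footnote 2 schedules one follow-up PET-CT, at 6 months, and leaves later ones to clinical indication. Footnote 4 says "Biopsies will be done only if clinically indicated". Footnote 11 lets the Principal Investigator waive follow-up assessments. Footnote 1 sets follow-up at 5 years.

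Section 2.2.1 names patterns of failure and disease-free survival as secondary comparisons. Section 12.0 compares disease-free survival by log-rank test but does not define it. In Section 9.2, progression at the target lesion rests on PET, with or without biopsy.

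**The concern.** The definitions leave no place for a target that has grown enough to meet LE but has had neither PET nor biopsy. It cannot be a Local Failure, because the second criterion is not met. Local Control is whatever is not Local Failure, so it is scored as controlled. A target that was never tested is then recorded in the same way as one that was tested and did not support failure.

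The error runs one way: missing confirmation can only move patients from failure to control. At stake is the patterns-of-failure comparison between the two regimens. Disease-free survival may also be affected, because progression at the target relies on the same tests. The bias would differ between arms if work-up of enlargement differed between them.

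**Working it through.** **The plan's own figures.** The documents give no power, sample size or expected rate for local control in this trial, so there is no planned figure to reproduce on this point. The only design figure is for toxicity (Section 12.0: 49 per arm, 81% power, achieved significance level 0.0037). Exact binomial enumeration of the stated one-sided continuity-corrected Z test with unpooled variance gives power 0.8053 and level 0.0037, so it reproduces. It does not depend on how local control is scored.

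**Step 1: classification under Section 9.2.**

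| Growth meets LE? | PET or biopsy result | Scored as |
|---|---|---|
| No | any or none | Local Control |
| Yes | supports failure | Local Failure |
| Yes | does not support failure | Local Control |
| Yes | neither done | Local Control |

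The last row is the gap.

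**Step 2: how much confirmation is scheduled.** Visits are at weeks 6 and 12, then 3-monthly for a year, then 6-monthly for 4 years. That is 2 + 3 + 8 = 13, or 2 + 4 + 8 = 14 if the 3-monthly year starts after week 12. One time point carries a scheduled PET-CT and none carries a scheduled biopsy. At 12 of 13 (or 13 of 14) visits, confirmation relies on clinical indication.

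**Step 3: illustration of size.** Let *f* be the true 2-year local failure proportion and *c* the proportion of failures that are confirmed. Ignoring deaths and censoring:

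- apparent local control = 1 − *f* × *c*
- failures scored as control, per arm = 49 × *f* × (1 − *c*)

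Inputs for *f* come from the background:

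- Section 1.1.3, single-dose series at 19-30 Gy: 2-year control 67.9%, so *f* = 32.1%.
- Section 1.1.3, single-dose series of mostly metastases: 2-year local progression-free rate 78%, so *f* = 22%.
- Section 1.1.2, three-fraction phase II trial: 2-year control 95%, so *f* = 5%.

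The documents give no value for *c*. I assume 0.75 and 0.50.

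| *f* | True failures per 49 | Scored as control, *c* = 0.75 | Scored as control, *c* = 0.50 | Apparent control (true → *c* = 0.75 → *c* = 0.50) |
|---|---|---|---|---|
| 32.1% | 15.7 | 3.9 | 7.9 | 67.9% → 75.9% → 84.0% |
| 22% | 10.8 | 2.7 | 5.4 | 78.0% → 83.5% → 89.0% |
| 5% | 2.5 | 0.6 | 1.2 | 95.0% → 96.3% → 97.5% |

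**Step 4: effect on the comparison.** Unequal work-up is not needed for the contrast to shrink. If *c* is the same in both arms, the apparent difference is *c* times the true one. With *c* = 0.50, a true difference of 32.1 − 5 = 27.1 points appears as about 13.5, and one of 22 − 5 = 17 points as 8.5.

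**The case against.** The strongest reply is that the gap may rarely open. Growth of 20% in a treated cancer is plausibly itself a clinical indication for PET or biopsy. The second criterion is worded as what *should* be found or done, which can be read as directing work-up. Section 1.2.2 says FDG-PET is in wide use for follow-up. This stands in part. A reader might infer that confirmation will often be missing, but no figure in the documents supports that. Equally, nothing in them requires the tests when LE is met.

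Requiring confirmation is also sound in itself, since treatment effect can mimic growth. That stands fully, and the fix keeps the requirement.

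Four stronger readings are tempting and should not be drawn.

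- *Sections 9.1 and 9.2 contradict each other.* Section 9.1 says of indeterminate consolidation that "it should be assumed that abnormalities are residual tumor". That sentence belongs to a paragraph on measuring the target when treatment effects blur its edges. It bears on size, the first criterion, and not on confirmation. The two steps are complementary.
- *PET is never scheduled.* One is, at 6 months. Only later PETs, and all biopsies, depend on indication.
- *The single-fraction arm will be misreported by the amounts shown.* The 32.1% comes from a stage I-II series in which 26-30 Gy gave significantly better control than lower doses (p = 0.032). The 22% comes from a series of 11 primary tumors and 48 metastases. Neither matches this population and dose. The three-fraction trial included central tumors, which are excluded here.
- *A treating oncologist who knows the arm decides who is tested.* The documents do not say who orders the tests, and Section 9.1 has a radiologist as well as a treating radiation oncologist review films. Different work-up by arm is possible but not shown.

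Reach is limited too. Local control is not itself named as an endpoint. The link to disease-free survival is inferred, because that endpoint is undefined. If death counts as an event, an untested enlargement delays the event rather than removing it.

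**Conclusion.** The point holds as a gap in classification. Followed exactly, Section 9.2 scores LE with neither PET nor biopsy as Local Control. The schedule makes such cases possible throughout 5 years of follow-up, and the resulting bias is always toward control. It affects the secondary patterns-of-failure comparison and possibly disease-free survival. It does not affect the primary toxicity endpoint or the sample size.

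Its size is unknown. On the assumption that 25% to 50% of true failures go unconfirmed, about 3 to 8 of 49 single-fraction patients and about 1 of 49 three-fraction patients would be misclassified at 2 years. These figures also assume that the cited failure rates carry over, that deaths can be ignored, and that no benign enlargement is confirmed as failure. They show scale and are not a forecast. This should be changed because it is cheap, not because the trial's main conclusion depends on it.

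**What to change.** In Section 9.2:

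- Keep Local Failure as defined. Nothing here calls for a change in how confirmed failures are dated.
- Restrict Local Control to targets with no LE, or with LE and a PET or biopsy that does not support failure.
- Add a third state, *LE, unconfirmed*: LE with neither PET nor biopsy. Report it separately by arm and do not count it as Local Control.

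In Section 12.0, add a sensitivity analysis of local failure that treats *LE, unconfirmed* as failure at the date of LE. Do the same for disease-free survival if target progression is to count as an event there, which Section 12.0 would need to state. Together with the analysis of confirmed failures, this brackets the effect of missing confirmation.

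The cost is two edits to the table and one added analysis, with no new tests. LE can be derived from the target measurements that Section 9.1 already requires at each follow-up imaging evaluation, so the category is only as complete as that imaging. The downside is that some unconfirmed LE will be treatment effect. Reported local control becomes less favorable, and the sensitivity analysis will count some benign enlargement as failure. That is why the category stands apart instead of being merged into Local Failure.

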10.0 ADVERSE EVENTS

Network sites refer to Appendix III for AE and SAE reporting instructions.

10.1 Adverse Events Reporting

Investigators are required by Federal Regulations to report serious adverse events to the Study Chair and Clinical Research Services. CRS will notify the Institutional Review Board if a patient has a reportable serious adverse event. This study will utilize the Common Toxicity Criteria version 3.0 to determine the severity of the reaction for adverse event reporting. (Appendix I)

Reporting requirements and procedures depend upon: (1) whether procedure is suspected of causing the adverse event, (2) whether the possibility of such an adverse event was reported in the protocol, consent form, or manufacturer's literature (expected or unexpected adverse event), (3) the severity or grade of the adverse event, (4) the phase of the study and attribution (the determination of whether an adverse event is related to a medical treatment or procedure). All reactions in a "reportable" category must be reported.

10.2 Serious Adverse Events (SAE)

- A serious adverse event (SAE) is any experience that suggests a significant hazard, contraindication, side effects or precaution. This includes any experience that:
- Results in death.
- Is a life-threatening adverse drug experience.
- Requires inpatient hospitalization or prolongation of existing hospitalization.

For the purpose of this study, hospitalizations for protocol-scheduled procedures, blood product transfusions, or for social reasons (i.e., awaiting transport home) will not be considered SAE's.

- Results in persistent or significant disability/incapacity.
- Is a congenital anomaly/birth defect.
- Requires medical or surgical intervention to prevent one of the outcomes listed above.

10.3 Reporting Serious Adverse Events

All serious adverse events will be reported to the IRB and Data Safety Monitoring Board according to the established guidelines. A cumulative summary of all adverse events occurring on this study will also be submitted to the IRB with the continuing review. Toxicity is reported, as required, to the FDA and study sponsors. All study data reviewed and discussed during these meetings will be kept confidential. Any breech in subject confidentiality will be reported to the IRB. In addition, all Roswell Park Cancer Institute initiated trials will be monitored periodically by the Compliance Monitor.

10.4 SAE Follow-up

For all SAE's occurring during the study or within 30 days of the last administration of study procedure, the investigator must submit follow-up reports the Study Chair and Clinical Research Services, CRS will notify Institutional Review Board regarding the patient's subsequent course until the SAE has subsided, or until the condition stabilizes, the patient dies, or receives alternative therapy.

Local reporting for data and safety monitoring for the protocol will require SAE's to be reported to the IRB, via the Clinical Research Service Office, using the Adverse Event Reporting form and the FDA MEDWATCH SAE reporting form.

On the anniversary date of the approved protocol at RPCI, the principal investigator will be required to report to the IRB the number of patients entered on the trial, the number of patients treated, a summary of all adverse events reported to date using CTC 3.0 grading, a specific list of serious adverse events requiring immediate reporting, and significant literature reporting developments that may affect the safety of participants or the ethics of the study.

11.0 DATA SAFETY AND MONITORING PLAN

- PI will assume primary responsibility for monitoring the progress of the trial and the safety of participants.
- Data will be submitted to the RPCI IRB annually for continuing review and at the completion of the study.
- Data integrity and protocol adherence are assured by regular data verification and protocol compliance checks performed by the research team (PI, research nurse, data manager and clinic nurse).

The IRB will review annual data and safety monitoring reports, as well as an interim analysis performed after 49 patients have been enrolled, and make recommendations on whether the study should continue unchanged, require

modification/amendment, or be closed based on unacceptable risk to participants.

12.0 STATISTICAL ANALYSIS

This is a phase II randomized study to compare incidence of RTOG grade 3 or higher toxicity associated with 2 different, established SBRT regimens for NSCLC.

Group sample sizes of 49 in group one (Gy x 3) and 49 in group two (Gy x 1) achieve 81% power to detect a difference between the group incidences of toxicity of 0.17. The incidence of toxicity in group one (the treatment group) is assumed to be 0.03 under the null hypothesis and 0.2000 under the alternative hypothesis. The proportion in group two (the control group) is 0.03. The test statistic used is the one-sided Z test with continuity correction and unpooled variance. The significance level of the test was targeted at 0.05. The significance level actually achieved by this design is 0.0037.

Descriptive statistics will be presented for each group. Incidence of toxicity will be compared using Z test. Disease free survival and overall survival will be compared between two groups using log-rank test statistics. Correlation analysis will be performed to explore the relationship between outcomes and toxicities with tumor biomarkers. The estimate of acute and long term toxicity associated with SBRT for NSCLC will be reported.

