A Phase II Randomized Study of 2 Stereotactic Body Radiation Therapy (SBRT) Regimens for Medically Inoperable Patients with Node Negative, Peripheral Non-Small Cell Lung Cancer

Protocol #: | 124407

Roswell Park Cancer Institute [name]

> Principal Investigator [name]

NCT#00843726

Final Version: 4/23/08 Amendment #1: 6/3/08 Amendment #2: 8/7/08 Amendment #3: 10/9/08 Amendment #4: 2/2/09 Amendment #5: 5/19/09 Amendment #6: 7/26/11 Amendment #7: 2/3/14 Amendment #8: 7/18/17

Network Investigator Signature Page

Protocol #: | 124407

A Phase II Randomized Study of 2 Stereotactic Body Radiation Therapy (SBRT) Regimens for Medically Inoperable Patients with Node Negative, Peripheral Non-Small Cell Lung Cancer

PROTOCOL APPROVAL AND INVESTIGATOR AGREEMENT

I have read and familiarized myself with this protocol and I agree to conduct the study as described according to GCP and ICH guidelines.

Principal Investig	gator		
Signed		Date	
Printed			
Address:			
Phone:			
Fax:			
E-mail:			

NOTE: Please see Appendix III for Network-specific instructions that will apply to your site.

ABSTRACT

- Principal Investigator: [name].
- **Co-Investigators:** [name]; [name]; [name]; [name]; [name], MD; [name]; [name]; [name] and [name]
- Phase: II Randomized
- **Objectives:** To determine the incidence of RTOG grade 3 or higher toxicity with 2 different radiation therapy regimens.
- Treatment Overview: Randomized between 30 Gy once or 20 Gy x 3.
- Eligibility Criteria: Medically inoperable patients with node negative, peripherally located, histologically proven NSCLC ≤ 5 cm are eligible.
- **Subjects and target study duration:** The trial will accrue 98 patients over 12 years.
- Endpoints: Incidence of RTOG grade 3 or higher toxicity, overall survival, correlations between blood and serum markers and survival and toxicity.

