Based on the early experience from Indiana University³¹, the Radiation Therapy Oncology Group (RTOG) opened a prospective trial of SBRT in 2004 (RTOG study 0236.) This study enrolled 52 medically inoperable patients with peripherally located, node negative NSCLC measuring <5cm. Patients received three 20 Gy fractions over 10-14 days. The trial was closed to accrual in October 2006. Early results in abstract form show 15% grade 3-4 toxicity. Specifically, with median follow-up of 8.7 months, there was one (2%) grade 4 and 7 (13%) grade 3 pulmonary/upper respiratory adverse events reported as related to protocol treatment. Two of the 7 pts reported pulmonary function test decreased, 1 pt reported cough/dyspnea, 1 pt reported hypoxia, 1 pt reported pneumonitis, 1 pt reported cough/forced expiratory volume, and 1 pt reported pneumothorax. There was also a grade 3 dermatitis and a grade 3 syncope reported as related to protocol treatment. No treatment related deaths have been reported³². As the median time to toxicity was previously reported to be 10.5 months in the previous Timmerman publication³⁰, the observed toxicity reported in this RTOG abstract (with only 8.7 months of follow-up) can be expected to rise.

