1.1.4 Rationale for the Current Study Design

From the aforementioned studies, we can conclude that single fraction and multi-fraction SBRT regimens are feasible and yield excellent local control. Most studies have used the multi-fraction regimen and no prior study has compared the two regimens in terms of efficacy and toxicity.

With multi-fraction regimens, the severe toxicity of 17% for those with peripheral lesions reported by Indiana University³⁰ is greater than suggested by the data summarized in section 1.1.1, which includes previous data from Indiana. For this reason, even in patients with peripheral lesions, it is imperative that SBRT be performed in the setting of a clinical trial (as opposed to routine clinical practice) so that the true incidence of toxicity can be captured and reported.

Of interest, no studies have yet shown major toxicity with single fraction regimens of 30 Gy. However, toxicities have been more rigorously monitored and reported in studies of multi-fraction regimens.

Given excellent reported control rates for both regimens, and absent any significant reported toxicity for single fraction therapy, a comparison of 30 Gy in one fraction versus 60 Gy in 3 fractions is warranted. Comparison of these regimens via a randomized prospective trial will allow for collection of a wealth of valuable information including, but not limited to, toxicity, outcomes, cost, patient comfort, and radiobiologic and dosimetric comparisons.

Interestingly, the Radiation Therapy Oncology Group (RTOG,) has chosen not to pursue single fraction regimens. Even, for central lesions where toxicity is high with the RTOG's preferred 20 Gy x 3 regimen, currently planned studies hope to reduce toxicity by increasing the number of fractions and reducing dose. A similar strategy appears to taking hold in

Japan. Certainly, reimbursement is less for a single fraction treatment and the effect of this variable is difficult to ascertain. Only in Germany does there appear to be interest in single fraction regimens. Consequently, it appears unlikely that many other institutions would be interested in the study design proposed here.

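### Cheap improvement, not an error: the planned toxicity test uses little of its 0.05 level; Boschloo's exact test, if fixed before arm data are seen, gives 84.8% power instead of 80.5% on the same 98 patients

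*Combined protocol and SAP*

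**What the plan says.** Section 12.0, repeated in the abstract, sizes the trial on the incidence of grade 3 or higher toxicity: "Group sample sizes of 49 in group one (Gy x 3) and 49 in group two (Gy x 1) achieve 81% power". The rates are 0.20 in group one (multi-fraction) against 0.03 in group two (single fraction), with 0.03 in both under the null. On the test: "The test statistic used is the one-sided Z test with continuity correction and unpooled variance". On its level: "The significance level of the test was targeted at 0.05", followed by an achieved level of 0.0037. The next paragraph describes the analysis more briefly: "Incidence of toxicity will be compared using Z test".

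Other relevant places:

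- Abstract: "The trial will accrue 98 patients over 12 years".
- Section 11.0: the principal investigator has primary responsibility for monitoring safety, the research team checks the data, and the IRB reviews "an interim analysis performed after 49 patients have been enrolled".
- Section 1.1.4 cites "the severe toxicity of 17% for those with peripheral lesions" with multi-fraction treatment. Section 1.1.2 reports of the cooperative-group multi-fraction trial: "Early results in abstract form show 15% grade 3-4 toxicity". Both figures lie below the design's 20%.

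**The concern.** The plan's own numbers show a gap between the error rate it allows itself (0.05) and the one it uses at its design null (0.0037). With about 49 × 0.03 = 1.5 expected events in the single-fraction arm, the continuity correction makes the rejection rule strict. Power is only about half a point above 80%, and the sample-size paragraph makes no allowance for non-evaluable patients. In a trial whose primary purpose is to compare toxicity, a missed excess is the costly mistake. A test that recovers part of the unused level and still guarantees 0.05 therefore deserves a look.

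**Working it through.** **Inputs (section 12.0).** n = 49 per arm; p1 = 0.20, p2 = 0.03 under the alternative; 0.03 in both arms under the null; one-sided target 0.05. Every patient is taken as evaluable.

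**Method.** List all 50 × 50 = 2,500 outcomes (x1, x2). Each has probability Bin(x1; 49, p1) × Bin(x2; 49, p2). Sum over the outcomes a test rejects.

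**Step 1: reproduce the plan.** Reject if Z = (x1/49 − x2/49 − 1/49) / √{[p̂1(1−p̂1) + p̂2(1−p̂2)]/49} > 1.645.

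- 5 vs 0: 0.0816/0.0432 = 1.89, reject.
- 4 vs 0: 0.0612/0.0391 = 1.57, do not reject.
- 6 vs 1: 0.0816/0.0510 = 1.60, do not reject.

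The rule rejects 896 outcomes. Power is 0.8053 (stated 81%). The level at 3% is 0.00372 (stated 0.0037). The maximum level is 0.0404, at a common rate of 0.45.

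**Step 2: Boschloo's test.** Order the outcomes by one-sided Fisher p. Take the largest cut-off whose rejection probability stays at or below 0.05 at every common rate. That cut-off is 0.0693 (maximum level 0.0478); the next possible cut-off gives 0.0502. It rejects 919 outcomes. None is rejected by the planned test only, so 919 − 896 = 23 are added, and Boschloo's power is never lower at any pair of rates.

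**Step 3: compare.**

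| Quantity | Planned | Boschloo |
|---|---|---|
| Power, 20% vs 3% | 80.5% | 84.8% |
| Power, 17% vs 3% | 66.8% | 73.3% |
| Power, 15% vs 3% | 55.1% | 63.2% |
| Level, both 3% | 0.0037 | 0.0145 |
| Level, both 5% | 0.011 | 0.027 |
| Level, both 10% | 0.024 | 0.035 |
| Maximum level | 0.040 | 0.048 |
| Multi-fraction rate with 80% power against 3% | 19.9% | 18.6% |
| Multi-fraction events needed against 0, 1, 2, 3 | 5, 7, 8, 10 | 4, 6, 8, 9 |

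**Step 4: where gain and cost arise.** At the design rates the added outcomes contribute 0.0208 (6 vs 1), 0.0171 (9 vs 3) and 0.0033 (4 vs 0). That is 0.0412 of the total 0.8479 − 0.8053 = 0.0426. At the 3% null, 4 vs 0 alone has probability C(49,4) × 0.03⁴ × 0.97⁹⁴ = 0.0098. This is most of the added level, 0.0145 − 0.0037 = 0.0108.

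**Step 5: scale.** The planned test has power 0.8432 with 53 per arm and 0.8515 with 54. Matching Boschloo by enrolment therefore takes 2 × (54 − 49) = 10 more patients. As an assumed range for losses: 48 per arm gives 79.5% vs 84.0%, and 44 per arm gives 74.6% vs 80.2%.

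**Step 6: the interim look.** Suppose, as an assumption, that it formally tests the arms with the planned Z test at one-sided 0.05, with 49 patients split 25/24 or 24/25. The maximum overall level is then 0.059 with the planned final test, reached at common rates of about 41% or 59%. With Boschloo it is 0.066, reached at 32% or 68%. At lower common rates Boschloo's overall level is 0.015–0.016 at 3%, 0.028–0.031 at 5% and 0.043–0.047 at 10%.

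**The case against.** **This is a preference.** The plan discloses both the 0.05 target and the 0.0037, its power exceeds 80% at its own design rates, and Boschloo makes a false positive at 3% about four times as likely. That stands: a sponsor who prefers the stricter rule can keep it. But 0.05 is the sponsor's own target, and Boschloo stays inside it at every common rate. Simply dropping the continuity correction would not: it gives 89.2% power, but its level peaks at 0.0598.

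**The opening may have passed.** The title page runs from a final version of 4/23/08 to Amendment 8 of 7/18/17. One-day and multi-day treatment cannot look alike to staff, the study team monitors safety and data, and an interim analysis is planned. The documents do not say that arm data have been seen, but they describe nothing that would prevent it. This is the main limit on the point.

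**Stronger readings that the documents do not support.**

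- *The gap between 0.0037 and 0.05 is a mistake.* It is not. 0.0037 is the correct exact level of the stated test at 3%.
- *The short analysis sentence leaves the test undefined.* The full form stands in the paragraph directly above, so this is brevity and not a contradiction.
- *The interim look undermines Boschloo in particular.* Section 11.0 describes an IRB review on continuing, modifying or closing the study for unacceptable risk, and mentions no formal test between arms. If there were one as assumed in step 6, either final test could exceed 0.05, and Boschloo's level at 3% would hardly move.

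**The gain is limited.** At 17% and 15% power improves but stays below 80%. Section 1.1.2 itself expects the 15% to rise with follow-up. Neither test uses the stratification by performance status and centre, so the change gains nothing there.

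**Conclusion.** The planned test is valid and correctly described. An available improvement is 4.3 points of power at the design rates (80.5% to 84.8%), 6.5 points at 17% and 8.1 points at 15%, each against 3%. The cost is a level at the 3% null of 0.0145 instead of 0.0037, with the maximum rising from 0.040 to 0.048. These figures rest on 49 evaluable patients per arm, a one-sided test for higher toxicity in group one, and no formal interim test between arms. The arithmetic is firm. Whether the change can still be made as a primary analysis depends on whether outcome data by arm have been seen, which the documents do not settle. It is optional.

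**What to change.** First, the sponsor should confirm whether outcome data by arm have been seen, and state in section 11.0 whether the interim analysis formally tests the arms.

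**If arm data are unseen:** in section 12.0 and the abstract, replace the test sentence and the later short sentence with:

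> Toxicity incidence will be compared by Boschloo's exact unconditional test at one-sided 0.05, alternative: higher incidence in group one (20 Gy x 3).

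Restate power as 85% (84.8%) and the level as 0.0145 at a common 3% rate, at most 0.048 at any common rate, assuming 98 evaluable patients and no formal interim test between arms.

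**If arm data have been seen:** keep the planned test as primary and report Boschloo only as a labelled sensitivity analysis. Repeating the full form of the Z test in the short analysis sentence would be tidy but is not essential.

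**Cost:** amended wording in section 12.0 and the abstract, and one clarifying sentence in section 11.0. No added patients, visits or data. The statistical price is the higher false-positive rate at low common toxicity rates, mostly from rejecting at 4 vs 0.
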